Women will be asked to complete the self-administered study questionnaires prior to the in-person baseline visit. They will be provided a link via email to the online questionnaires or given a hard copy version if preferred.

Assessments	Screening	Baseline	Post-chemo	1-year	2-year	5-year
Screening Questionnaire	X					
Demographic Questionnaire*		X				
Medical History Questionnaire*		X				
Food Frequency Questionnaire		X	X	X	X	X

Phone assessment 24-hour dietary recall – 1-day ^{&1}		X	X	X	X	
Physical Activity Questionnaire		X	X	X	X	X
Patient Global Assessment (SGPGA)	X					
PROMIS quality of life questionnaires(74)		X	X	X	X	X
Prescription Medication		X	X	X	X	X
Adherence to medication questionnaire(75, 76)				X	X	X
Neuropathy – EORTLC QLQ-CIPN20(77)		X	X	X	X	X
Work history			X	X	X	X
Beliefs about Medication Questionnaire(78)				X	X	X
Treatment Satisfaction Questionnaire for Medication(79)				X	X	X
Health Insurance, prescription coverage and prescription refill habits				X	X	X
Medication usage questionnaire				X	X	X
Aromatase Inhibitor/Tamoxifen usage form				X	X	X
Breast Cancer Prevention Trial (BCPT) Symptom Scales (80)		X	X	X	X	X
Brief Pain Index		X	X	X	X	X
Homunculus		X	X	X	X	X
Y5-Lymphedema Questionnaire						X
Supplement intake/over the counter medication *		X	X	X	X	X
Y1 -Lymphedema Questionnaire				X		
Y2- Lymphedema Questionnaire					X	
Satisfaction Questionnaire (Intervention group)				X		
Side-effects and toxicity assessment (PRO-CTCAE™)		X	X			
Chemotherapy delay/dose reduction/reasons (extracted from EPIC EMR)			X			
Grip Strength [%]		X	X	X	X	
EPIC 2YR follow up treatment form					X	

EPIC 5 Year medical usage and breast cancer status abstraction						X
Two Year Follow up Treatment form'					X	
Height and weight measured [%]		X	X	X	X	
Waist and hip circumference measured [%]		X	X	X	X	
Blood collection [%]		X	X	X	X	
DXA scan [%]		X	X	X	X	
Urine collection ^{%@}				X	X	
Urine collection for pregnancy test if applicable prior to DEXA [%]		X	X	X	X	
Stool collection [%]		X	X	X		
Skin carotenoids [%]		X	X	X	X	

*: Part of the Baseline Questionnaire

%: Applicable only to the Yale site when in-person visits are completed. Assessments are optional.

@ Applicable to women who are prescribed an aromatase inhibitor

&: Assessment is optional.

1: Discontinued in August 2020.

Note: As of mid-March 2020, in-person visits and associated in-person assessments (DXA, blood and urine collection, weight/height and waist hip measurements, skin carotenoids, stool collection, grip strength) could no longer be conducted due to the coronavirus pandemic. In-person visits and assessment will re-start when allowed by the institution.

Screening Questionnaire: Eligibility criteria will be determined from electronic medical records via EPIC and/or via interview-administered questionnaire during the screening visit.

Screening will include determining eligibility on diet and physical activity by asking the following questions:

1. 'Prior to your diagnosis of breast cancer, did you exercise, *(for example, jogging, walking on a treadmill or stationary bicycling)?'

If the patient reports exercising less than 150min/wk moderate aerobic exercise and less than 75 min/wk of vigorous aerobic exercise (e.g. running) or an equivalent combination they are coded 'no' on the exercise criteria

- 2a. 'Prior to your diagnosis of breast cancer, how many servings of vegetables did you usually eat per day (don't include French fries)?'
- 2b. 'Prior to your diagnosis of breast cancer, how many servings of fruit did you usually eat per day?'

A card describing serving sizes will be provided for the patient's reference.

Eligibility Criteria for fruit and vegetable intake: < 7 fruit and vegetables combined per day
If the patient reports eating less than 7 fruits and vegetables per day, they are coded 'no' on the healthy eating criteria

To be eligible, participants need to respond 'No' to both questions.

These two guidelines have been used as screening criteria in other diet and physical activity trials. (81, 82)

In addition, we will administer the Patient-Generated Subjective Global Assessment (PG-SGA) (83). If malnourished a patient will be ineligible for the study.

All patients who are screened by phone following receipt of MD consent to contact and who are ineligible for the study or do not wish to participate in the LEANer study, will be asked if they would be willing to be contacted about participation in future studies.

Medical history and demographic questionnaires: The following will be assessed via questionnaire prior to enrollment and at 1- 2- and 5-years (when applicable): reproductive and menstrual history, medical history, family history of breast and other specific cancers, and history of tobacco and alcohol. Menopausal status will be defined at diagnosis as 12 months of amenorrhea; perimenopause will be defined as amenorrhea for 3 months in the previous 12 months. Self-report of menses is viewed as reliable to define menopausal status, especially since serum hormonal levels are highly unreliable in the perimenopausal transition phase. To confirm therapy and other treatments, the following will be abstracted from medical records via EPIC: surgery, presence or number of involved axillary lymph nodes, hormone receptor status, disease stage, tumor size, chemotherapy therapy and evidence of completion (see also our section on chemotherapy completion rate); type of endocrine therapy (if applicable) including start date (see section on Adherence to Endocrine Therapy). All current prescription and over-the-counter medications will also be inventoried.

Physical Activity: Women will complete a physical activity questionnaire to assess current (past week) and past year (i.e., year before diagnosis) physical activity levels. Hours/week spent in different types and intensities of activity (including sedentary time) will be computed over the past week and year before diagnosis, as well as at 1-year 2-year and 5-year follow ups.. This physical activity questionnaire has been used in all of [name] previous studies and has been extensively published and shown to be valid and reliable.(19) Women randomized to intervention will be given Fitbit devices which will be used as an objective measurement of physical activity. Participants will wear the Fitbits and they will be encouraged to wear the Fitbit at all times and record the steps per day in their LEANer log.

Dietary Intake: Women will complete a 120-item food frequency questionnaire (FFQ) which was developed for the Women's Health Initiative Study and has been validated against 4-Day Food Records and 24-hour Dietary Recalls (discontinued August 2020).(84) FFQs will be administered at baseline, post-chemotherapy, 1- and 2-years. The FFQ will be completed at the 5-year follow up. Subjects will have the option of completing an online version of the questionnaire. A link will be sent to the subject

to allow completion. No PHI will be collected by the Fred Hutchinson Cancer Research Center who oversee collection of the FFQ data. No IP addresses are accessed/collected.

Adherence will be assessed via attendance to counseling sessions, as well as by adherence to the diet and physical activity recommendations (assessed via questionnaire at baseline, 1, and 2 years). Women randomized to intervention will also complete a daily log book where they log their daily food, beverages and physical activity (similar to our LEAN and HOPE studies). At each counseling session, the dietitian will review the log book either in person or via phone reporting.

*Weight and Height: Weight and height will be measured by research staff at baseline, post chemotherapy, 1- and 2-years. Participants will be weighed in light clothing, without shoes, rounding up to the nearest 0.1 kg; height will be measured in a standard manner, without shoes, using a stadiometer, rounding up to the nearest 0.1 cm. (Yale in-person visit only)

*Waist and Hip circumference: Waist and hip circumference will be measured at baseline, post-chemotherapy, 1- and 2- years. Each measurement will be taken twice by a research member. (Yale in-person visit only)

*Grip strength will be measured by a simple to administer modified sphygmomanometer (Detecto DHS Series, Northbrook, Illinois). The participant will be asked to squeeze the balloon of the sphygmomanometer three times with maximal force. The average value of three trials for each hand will be recorded. Higher scores (reported in kPa) reflect better grip strength. (Yale in-person visit only)

Pain: Pain will be assessed using the Brief Pain Index (85). Arthralgia will be assessed using a self-assessment tool where patients are asked to mark 'yes' were asked to mark painful joints on a homunculus with circles showing upper and lower extremity joints, and four areas of the back and neck, and additional diagrams of both hands (three joints on each finger and thumb) and both feet (joints at the base of each toe). (76).

Body Image: Body image will be assessed using the PROMIS assessment.

Supplement intake/over the counter medication: These will be assessed using a questionnaire used in prior studies overseen by [name].

Prescription medication: Patients will be asked to self-report current prescription medication usage.

*Dual Energy X-Ray Absorptiometry (DEXA) scans: DEXA scans will be used to assess body fat percentage, LBM and bone mineral density at baseline, post-chemotherapy, 1- and 2-years. The DEXA measurements will be made with a Hologic scanner (Hologic 4500 with a "Discovery" upgrade, Hologic Inc, Waltham, Mass). All DEXA scans will be evaluated by a radiologist who will be blinded to the intervention group of the participant, and a quality control phantom will be used daily for calibration. Women of childbearing potential will be required to complete a pregnancy test prior to the DEXA scan. Women who are pregnant or intend to get pregnant during the 2-year study time period are excluded from the study. Women who can get pregnant will have a pregnancy test prior to each DEXA scan, if the pregnancy test is positive the woman will not be able to enroll in the study or, if already enrolled, will no

longer be able to participate in the study. However, the data collected prior to pregnancy will be included in the study. (Yale in-person visit only)

Quality of Life (QOL): Women will complete the PROMIS questionnaire to assess physical, emotional, social, and functional well-being as well as fatigue and overall quality of life (74) ,at baseline, post-chemotherapy, 1- 2- and 5-years. (86) They will also complete the EORTLC QLQ- CIPN20 to assess peripheral neuropathy (77), the Breast Cancer Prevention Trial Symptoms Checklist

Work History: Women will complete a questionnaire on work history which can be impacted by chemotherapy (87).

Medical Usage: At the Year 5 timepoint, the following data will be abstracted from the EPIC EMR: breast cancer recurrence, second primary breast cancer, weight, health care utilization.

*Skin carotenoid assessment: Reflectance Spectrometry (RS) is a quick novel noninvasive method of assessing skin carotenoids(88). Skin carotenoids measures will be conducted at the baseline, post-chemotherapy, 1-year and 2 year visits. The patient will apply gentle pressure on their thumb against the RS lens for less than one minute. Each patient's thumb will be scanned three times. RS values will be recorded on the laptop connected to the instrument. The RS methodology uses a broadband white light to measure skin carotenoids and other chromophores like melanin and hemoglobin directly through their respective absorptions. The reflected light is directed to a spectrograph coupled with a room-temperature detector array. The data processing algorithm corrects for the potentially confounding effects of melanin and tissue scattering (88). (Yale in-person visit only)

Side-effects and toxicity assessment: Women will complete the Patient-Reported Outcomes Version of the Common Terminology Criteria for Adverse Events (PRO-CTCAE™) at the BL and post-chemotherapy visits (https://healthcaresdelivery.cancer.gov/pro-ctcae/terms_of_use.html).

Lymphedema: Women will be screened for lymphedema the 1-year 2-year and 5-year follow ups by asking the following question ‘Since your cancer treatment, have you had any swelling on the same side as your treatment that has not gone away?’ If the response is ‘Yes’ then she will be asked about diagnosis of lymphedema and will complete the Norman Lymphedema Questionnaire. If lymphedema is reported any woman randomized to intervention, she will be instructed to wear a compression sleeve on the affected arm while strength training, and the upper body strength training will follow the model developed by Schmitz et al, in order to avoid lymphedema exacerbations. (89) These exercise protocols have been used by us before and are consistent with recommendations from the American College of Sports Medicine for cancer survivors.(89)

*Biomarkers: Fasting blood (> 12 hours) will be collected at baseline, at completion of chemotherapy and at the 1- and 2-year clinic visit. (Yale in-person visit only) Two 10-ml red-top tubes will be collected for serum, and two 10-ml lavender-top tubes will be collected for EDTA plasma. Technicians will centrifuge the EDTA samples at 2,000 rpm for 15 minutes at 4°C within 1 hour of collection. Plasma and buffy coat will be separated and, along with the serum, will be transferred into cryovials and labeled with freezer-proof labels with participant ID #s and date. All specimens will be stored temporarily at 4°C after aliquotting prior to delivery to our freezer (within 2 days), and then stored at -80

degrees C until analysis. Each woman's baseline and follow-up samples will be assayed in the same batch, and an equal number of intervention and control samples also will be included in each batch. Appropriate blinded quality control samples (low and high levels) will be used to monitor the reliability of each assay.

Insulin will be measured in serum using an enzyme-linked immunosorbent assay (ELISA) kit (DSL-10-1600, Diagnostic Systems Laboratories, Inc., Webster, TX). *CRP* will be measured with direct chemiluminescent immunoassay on the Immulite analyzer (Diagnostic Products Corporation (DPC, Los Angeles, CA). *NCSI* levels will be analyzed in [name] laboratory at the YSM. In addition, a panel of over 200 proteins potentially related to neuropathy will be analyzed at MD Anderson Cancer Center.

Immune markers

Olink: 92 inflammation, immuno-oncology, and metabolism proteins will be measured in blood plasma samples using Olink Biosciences's multiplex proximity extension assay (PEA). The 96 protein targets include cytokines, chemokines, markers that have been implicated in immunotherapy response (e.g., PD-L1, LAG3), and tumor or immune cell metabolism (e.g., ARG1, FBP1). Protein levels will be expressed as normalized protein expression and \log_2 transformed prior to statistical analysis. The protein levels in the intervention group will be compared with standard of care controls.

RNAseq: mRNA will be extracted from buffy coats using the RNeasy Plus Kit (Qiagen) according to the manufacturer's instructions. RNA sequencing will be performed at the Yale Center for Genome Analysis (YCGA). Gene expression differences between intervention and standard of care samples will be determined using "DESeq2" R package.

Genome Wide Methylation for EAA

The MethylationEPIC BeadChip (Illumina; San Diego, CA) will allow us to interrogate >800,000, methylation sites quantitatively across the genome at the Yale Center for Genome Analysis. A sample of pooled female DNA is routinely included on each BeadChip as a control throughout the experiment and assessed for reproducibility using a Pearson R² coefficient. We will set to missing data points with detection p-values >.001 and will exclude any samples with probe detection call rates < 95% as well as those with an average intensity value of either <50% of the experiment-wide sample mean or < 2000 arbitrary units (AU). To limit confounding due to positional effects, samples for each person will be run in the same row.

P16 Human p16 ELISA Kit (LSBio) will be used according to manufacturer's instructions.

***Stool collection:** A stool collection kit, collection and mailing instructions will be provided to each participant to collect a stool sample in their home as baseline, post chemo and 1-year. Stool will be returned by pre-paid Fed Ex delivery to the Yale School of Public Health. Samples will be frozen and then sent for analysis to outside laboratories (Metabolon and [name] at UCSD). Women who are randomized after their first chemotherapy session (but prior to their second session) will not be asked to complete the stool collection at baseline or thereafter as their stool microbiota may have been affected by the chemotherapy so change in microbiota would be uninterpretable.

Analysis of Chemotherapy Completion Rate: Chemotherapy completion rate will be assessed (via medical records in EPIC) as the average relative dose-intensity (RDI) for the originally planned regimen

based on standard formulas. We will measure the number and percent of patients requiring dose-adjustments, who have dose-delays, the reason for the dose-adjustment/dose delays (e.g. neuropathy or vacation) and the percent dose reduction for each participant and by group, similar to Courneya and van Waart's papers.(8, 9) All relevant data will be extracted from EPIC (electronic medical records).

Analysis of Pathologic Complete Response: Pathology reports will be used to evaluate residual tumor after neoadjuvant chemotherapy. Pathologic complete response will be defined as no evidence of viable invasive tumor cells at the primary tumor site and axillary lymph nodes in the surgical specimen, regardless of the presence of non-invasive breast cancer or DCIS (Tis); i.e., yT0/TisN0.

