- a. Does your YNHH privilege delineation currently include the **specific procedure** that you will perform? Yes No
- b. Will you be using any new equipment or equipment that you have not used in the past for this procedure? Yes No
- c. Will a novel approach using existing equipment be applied? Yes No

If you answered "no" to question 4a, or "yes" to question 4b or c, please contact the YNHH Department of Physician Services ([name]) for prior approval before commencing with your research protocol.

IMPORTANT REMINDER ABOUT RESEARCH AT YNHH

Please note that if this protocol includes Yale-New Haven Hospital patients, including patients at the HRU, the Principal Investigator and any co-investigators who are physicians or mid-level practitioners (includes PAs, APRNs, psychologists and speech pathologists) who may have direct patient contact with patients on YNHH premises must have medical staff appointment and appropriate clinical privileges at YNHH. If you are uncertain whether the study personnel meet the criteria, please telephone the Physician Services Department at [contact]. **By submitting this protocol as a PI, you attest that you and any co-investigator who may have patient contact has a medical staff appointment and appropriate clinical privileges at YNHH.**

SECTION I: RESEARCH PLAN

1. **Statement of Purpose:** State the scientific aim(s) of the study, or the hypotheses to be tested.

We propose to examine, in 172 women newly diagnosed with Stage I-III breast cancer who are not practicing the dietary and lifestyle guidelines, and who will receive neoadjuvant or adjuvant chemotherapy as part of their treatment, the effect of a 1-year dietary and physical activity guidelines intervention vs. usual care on the breast cancer outcomes described below. Women will be enrolled either before beginning chemotherapy or following the first chemotherapy infusion but prior to the second chemotherapy infusion (Time 0). Follow up visits will occur post chemotherapy (Time 1), at one-year post-diagnosis (Time 2), at two years post-diagnosis (Time 3) and at five years post-diagnosis.

Primary Endpoints: Adherence to Breast Cancer Treatments

Aim 1a: Chemotherapy completion rates (dose amount, number of dose reductions and dose delays)

Aim 1b: Adherence to endocrine therapy in women taking tamoxifen or Aromatase Inhibitors (AIs) at 12- and 24-months after enrollment

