Secondary Endpoints: Changes in Biomarkers, Body Composition, Quality of life, pathological complete response (pCR).

Aim 2a: Neuronal calcium sensor 1 (NCS1), Insulin and C-reactive protein (CRP) levels

Aim 2b: Body composition (body weight, BMI, body fat, lean body mass and bone mineral density)

Aim 2c: Changes in Quality of Life (QOL) including cognition

Aim 3: Change in the fecal microbiome

Aim 4a: Determine the association between skin carotenoids pre- and post-chemotherapy and the side effects of chemotherapy (e.g. nausea, neuropathy) in the usual care group.

Aim 4b: Examine the difference in the pre- to post-chemotherapy change in skin carotenoid levels between women randomized to intervention vs. usual care.

Aim 5: Determine pCR, defined as no evidence of viable invasive tumor cells at the primary tumor site and axillary lymph nodes in the surgical specimen, in patients receiving neoadjuvant chemotherapy.

Aim 6: Determine the effect of the coronavirus pandemic on diet, physical activity, cancer care and mental health of LEANer participants.

Exploratory Endpoints:

- Examine the difference in the pre- to post-chemotherapy change in blood-based immune markers between women randomized to intervention vs. usual care.
- Examine changes in epigenetic age acceleration (based on epigenetic clocks using >800,000, methylation sites quantitatively across the genome) and p16, both as biomarkers of aging, from baseline to post-chemotherapy in usual care women
- Evaluate the effect of the lifestyle intervention vs. usual care on change in epigenetic age acceleration and p16 from baseline to one-year.
- Determine the effect of the intervention on longer term (5-year) physical activity, diet quality (healthy eating index) and quality of life.
- Determine breast cancer recurrence and second primary breast cancer.

2. **Background:** Describe the background information that led to the plan for this project. Provide references to support the expectation of obtaining useful scientific data.

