and increasing rates of breast conserving surgery (BCS) (68) Additionally, chemotherapy given prior to surgery allows for in vivo assessment of chemotherapy sensitivity. Patients who achieve a pathologic Complete Response (pCR), in which the tumor has been eradicated by chemotherapy prior to surgery such that there are no remaining viable invasive tumor cells at the primary tumor site and axillary lymph nodes in the surgical specimen, are known to have superior breast cancer-related and overall survival outcomes. (20) (21) Pathologic complete response rates have been used by the FDA to approve drugs; yet, there is a paucity of data regarding how lifestyle interventions affect this important outcome. Some studies have demonstrated that overweight/obese patients have a significantly lower pCR rate compared to patients who are normal/underweight (OR 0.67, 95% CI 0.45-0.99.), while other studies have found that overweight/obese women have lower pCR rates in ER+/HER2+ cancers but higher pCR rates in ER-/HER2+ cancers. (22) Our study will allow us to investigate pCR rates in those who receive a healthy diet and physical activity intervention compared to those who do not. Further, we will control for meaningful covariates including initial BMI, chemotherapy regimen and completion rates, and tumor receptor status. There is a recognized need to evaluate the functional, endocrinologic, and immunologic end points associated with lifestyle modifications and the effects of these on response to therapy. (23)

Lifestyle Interventions and Cancer Biomarkers in Breast Cancer Survivors: We recently completed the Lifestyle, Exercise and Nutrition (LEAN) 6-month randomized trial of healthy eating and exercise in 100 women (of 825 screened, 12%) who had completed treatment for breast cancer. (24) The 11-session intervention (conducted in person or via telephone) was adapted from the 2010 U.S. Dietary Guidelines, ACS and AICR guidelines 1-3 and modeled on the diabetes prevention program. We found statistically significant decreases in body weight among women randomized to intervention (-6% mean weight loss) compared to usual care (-2.0% mean weight loss) ($p = .0024$), and a 30% decrease in CRP ($p = .05$) and 10% decrease in insulin ($p = 0.08$) compared with no changes in usual care. Favorable dietary changes were observed as well (see Goals of Intervention section for results on page 10).

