In July 2020, all women who are or who have been (if they agreed to future contact as indicated on the study consent form) participants in LEANer will be invited via email to complete an online or hard copy survey regarding the effect of the coronavirus epidemic on their cancer care, and their mental health, diet and physical activity. A link to the survey, which will be hosted on the Qualtrics platform, will be included in the email invitation with instructions on how to get the hard copy questionnaire if desired. The survey will take approximately 10-15 minutes to complete. A study staff member will follow up by email, text message or phone to confirm receipt of the invitation to complete the survey and answer any questions.

Newsletter: A newsletter will be mailed to all participants at 6-monthly intervals while enrolled in the study informing them of the progress of the study and providing relevant information with regard to breast cancer survivorship issues.

All assessments denoted * above are conducted at the in-person visits and are optional.

d) Randomization: Participants will be randomized into one of 2 study arms using a random permuted block design of varying block size in a 1:1 ratio (N=125 to intervention, 125 to usual care). To ensure participants with similar characteristics are equivalently assigned to the 2 groups, we will stratify on the following factors that may be associated with some of the study endpoints:

- i) chemotherapy regimen (≤ 4 cycles vs. >4 cycles)
- ii) hormone receptor status (ER/PR+ or not)
- iii) HER2 status (HER2+ve or not)

Resulting in six strata.:

- a) HR/PR+ve, HER2-ve, ≤ 4 cycles
- b) HR/PR+ve, HER2-ve, >4 cycles
- c) HR/PR-ve, HER2-ve, ≤ 4 cycles
- d) HR/PR-ve, HER2-ve, >4 cycles
- e) HR/PR+ve, HER2+ve, >4 cycles
- f) HR/PR-ve, HER2+ve, >4 cycles

The following study personnel will be masked to participant study arm: clinic medical staff performing the DXA scan and laboratory analysis.

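### The adjusted pCR comparison controls for chemotherapy completion, a primary outcome settled mainly after randomization, so its arm effect is not the total effect of assignment

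*Combined protocol and SAP*

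**What the plan says.** The combined protocol and SAP covers this point in four places.

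- **Background, Lifestyle Interventions and Pathologic Outcomes.** The study will allow the team to "investigate pCR rates in those who receive a healthy diet and physical activity intervention compared to those who do not". The next sentence adds that "we will control for meaningful covariates including initial BMI, chemotherapy regimen and completion rates, and tumor receptor status".
- **Statement of Purpose.** The first primary item is "Aim 1a: Chemotherapy completion rates". pCR is secondary: "Aim 5: Determine pCR, defined as no evidence of viable invasive tumor cells at the primary tumor site" and in the axillary nodes, in women given neoadjuvant chemotherapy. Women enroll before chemotherapy or "following the first chemotherapy infusion but prior to the second chemotherapy infusion (Time 0").
- **Research Plan.** Completion is assessed "as the average relative dose-intensity (RDI) for the originally planned regimen". For pCR, "Pathology reports will be used to evaluate residual tumor after neoadjuvant chemotherapy"; the paragraph headed as the pCR analysis defines the outcome but names no model.
- **Section I.12, Statistical Considerations.** pCR does not appear. The model for secondary aims is a repeated-measures analysis of change from baseline. The general covariate list includes BMI at diagnosis, type of chemotherapy and hormone receptor status. It does not include completion or RDI, and it does not say that it replaces the Background sentence.

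**The concern.** The question posed for pCR is whether assignment to the intervention changes the response rate. Completion lies between assignment and response. If the intervention helps women receive more of their planned dose, and dose delivered helps clear the tumor, that benefit is part of the intervention's effect. Conditioning on completion takes it out.

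What remains is not reliably the effect by other routes either. Completion is not randomized. If an unmeasured factor such as frailty or comorbidity affects both completion and pCR, conditioning on completion makes the arms differ on that factor, and the adjusted estimate can move in either direction.

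The risk is a misreading: an adjusted odds ratio near 1 could be reported as no effect on pCR in a trial where the intervention worked through dose delivered.

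**Working it through.** **1. Timing.** At most one infusion precedes randomization. The Usual Care Group text gives 4 cycles for about one-third of women and 4 + 12 = 16 for about two-thirds.

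- 4 infusions: at most 1/4 = 25% before randomization, so at least 75% after.
- 16 infusions: at most 1/16 = 6.25% before, so at least 93.75% (about 94%) after.
- If every woman enrolled after her first infusion: (1/3)(25%) + (2/3)(6.25%) = 12.5% before on average.

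Section I.12 also counts dose reductions from T0 to T1. Completion is therefore mainly post-randomization, and in neoadjuvant women it precedes the surgical pathology.

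**2. Is completion meant to move?** Power and Sample Size Considerations: 86 per arm, difference 0.05, SD 0.10, two-sided 0.05. A two-sample t test gives 90.3% power, which agrees with the stated 90%. The powered shift is 0.05/0.10 = 0.5 SD of RDI.

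**3. Size of the path removed (illustration).** Assume a pCR odds ratio (OR) of 1.25, 1.5 or 2.0 per 0.10 RDI. The part carried by a 0.05 gain is exp(0.5 × ln OR):

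| Assumed OR per 0.10 RDI | Factor removed by adjustment |
|---|---|
| 1.25 | 1.118 |
| 1.5 | 1.225 |
| 2.0 | 1.414 |

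**4. Simulation (illustration).** Logistic model, 1,000,000 women per scenario. The RDI difference of 0.05 and SD of 0.10 come from the plan; everything else is assumed. The first two rows cover control pCR of 20%, 30% and 40%; the shared-cause rows use 30%. The shared cause shifts RDI by 0.05 per SD (correlation 0.05/0.10 = 0.5 with RDI within arm) and the pCR logit by +0.5 or −0.5.

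| Scenario | Unadjusted arm OR | Completion-adjusted arm OR |
|---|---|---|
| Direct OR 1.3, no shared cause | about 1.44–1.77 | about 1.30 |
| No direct effect, no shared cause | about 1.11–1.39 | about 1.00 |
| Direct OR 1.3, shared cause, same sign | about 1.42–1.65 | about 1.15 |
| Direct OR 1.3, shared cause, opposite sign | about 1.43–1.76 | about 1.45 |

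The unadjusted values can fall below the product of the direct OR and the step 3 factor (for example 1.3 × 1.414 = 1.84) because odds ratios are not collapsible.

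**5. Precision.** Suppose, generously, that all 172 women were neoadjuvant (86 per arm), with control pCR 30% and OR 1.44. Intervention odds = (0.30/0.70) × 1.44 = 0.617, so pCR = 38.2%. SE of ln OR = √[1/(86 × 0.30 × 0.70) + 1/(86 × 0.382 × 0.618)] = 0.323. The 95% CI is exp(0.365 ± 1.96 × 0.323), about 0.76 to 2.71. With 60 neoadjuvant women in total it is about 0.49 to 4.21. The shifts in step 4 lie inside these intervals.

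**The case against.** - **Location.** The sentence is in the Background, and the covariate list in Section I.12 omits completion, so a statistician working only from Section I.12 would not adjust for it. This makes it partly a matter of reconciling two places. But Section I.12 never mentions pCR, and its secondary-aims model of change from baseline does not suit a yes/no result read once. The Background sentence is the only text that names covariates for pCR.
- **The total effect may already be planned.** The plain arm comparison comes first and the adjustment is introduced as a further step. Adjustment also does not breach the rule of grouping women as randomized. Both points stand. They limit the concern to the adjusted result, but the plan does not say which result leads.
- **An effect beyond dose delivered is a legitimate question.** The Background summary expresses interest in mediating mechanisms. That supports keeping such a model, but labelled for what it is and with its no-shared-cause assumption stated.
- **The path is conditional.** If the intervention does not change RDI, no mediated benefit is lost. The 0.05 is a detectable difference, not an observed one, and the cited exercise evidence is mixed. The home-based low-intensity arm had the same share of dose adjustments as usual care (34% and 34%). RDI was 90% against 84% with resistance exercise (P = .033) and 87% against 84% with aerobic exercise (P = .266). This is why mediation is called plausible and not shown. A covariate set fixed in advance should still not depend on the primary aim failing.
- **The illustrative figures rest on assumptions.** Agreed. They show direction and order of size only.

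**Conclusion.** The concern holds. The covariate set stated for pCR contains a variable that is a primary outcome, is at least 75% to 94% determined after randomization when counted by planned infusions, and precedes the pathology read. The adjusted arm effect would not estimate the total effect of assignment, and it would isolate a direct effect only if completion and pCR shared no unmeasured causes.

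The amount of distortion cannot be derived from the documents. It depends on how far the intervention moves RDI, how strongly RDI relates to pCR, and on shared causes. Under the assumptions shown, the arm odds ratio loses a factor of about 1.12 to 1.41. That is smaller than the sampling uncertainty, so this is a problem of what the number means and not a demonstrable change of result.

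The scope is one secondary endpoint in the neoadjuvant subset. Initial BMI and receptor status are sound covariates, as is the regimen if taken as planned at baseline. The change should be made, but it does not threaten the trial's main conclusion.

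**What to change.** 1. In the Background paragraph on pathologic outcomes, remove completion rates from the covariates for pCR.
2. In Section I.12, state that pCR is compared by randomized arm among neoadjuvant women with logistic regression. Report the crude comparison first and an adjusted model as supportive, the order Section I.12 already uses for endocrine therapy adherence.
3. Limit adjustment to variables fixed at randomization: initial BMI, planned regimen or cycle stratum, hormone receptor status and HER2 status. The Randomization section says "we will stratify on the following factors that may be associated with some of the study endpoints", and the cycle stratum and the two receptor variables are those factors.
4. If a completion-adjusted pCR result is wanted, report it only as an exploratory mediation analysis, with the assumption of no unmeasured shared causes stated.

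The cost is a few words deleted and one or two sentences added. No new data, visits or sample size change are needed.
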